Clinical Optimization of Ambient Temperature and Heating Methods in Caring in Major Burns Patients

Optimal Heating Temperature in Major Burns Patients

MSN [name]

Universitat Rovira i Virgili
Sanidad Castilla y León
Hospital Universitario Rio Hortega Valladolid
Universidad de Valladolid
[contact]

Study Protocol, Statistical Analysis Plan (SAP), Informed Consent Form (ICF)

Version 1.0

Marchy, 2020

HeatingBurns01- Study Protocol, Statistical Analysis Plan (SAP), Informed Consent Form (ICF)

1. Material and methods

6.1 Design, methodology and justification:

Pre-experimental pre-experimental epidemiological study without control group, in large burnt patients that will evaluate the influence on the metabolic expenditure of the inclusion of active external overheating in the control of ambient temperature adjusted to thermal comfort.. Two methods of active external heating, thermal plate and convective air blanket shall be used. Metabolic expenditure shall be measured by indirect calorimetry in the usual treatment with passive external overheating and post-intervention in the combination of passive and active external warming.

Sand pre-study the combination of passive and active external overheating by measuring the operating temperature in various cases for optimal application, as well as the definition of thermal comfort in the unit of large burns. In this way, two study stages are integrated as shown in *Table 5.*.

Table 5: Study stages Clinical optimization of ambient temperature and heating methods in the care of the patient large burned according to thermal comfort

Stage 1	Stage 2
Empirical study of operating temperature according to the	Quasi-experimental study of large burned patients to study
combination of passive and active external heating methods for the definition of environmental comfort.	the impact on metabolic expenditure of the inclusion of active external overheating in environmental temperature
methods for the definition of environmental connoct.	control

6.2. Population and sample:

6.2.1. Target population

Burnt patients receiving treatment in large burnt units that require heating for the maintenance of normothermia and prevention of hypothermia. In 2017, 9186 burn hospitalizations were recorded, with a national incidence of 7 cases per 100,000 inhabitants.

6.2.2. Accessible population

Patients with thermal burns admitted to the burn unit of the Río Hortega Hospital in Valladolid since March 2020 who do not meet exclusion criteria. Sand reached 30 patients admitted in 2018 for thermal burns. Although the unit, a reference in Castile and León for the care of burn patients, serves a population of 2,419.00 inhabitants

6.2.3. Sampling design

Sampling in the selection of patients shall be per snowball, all participants in the centre shall be included until sample saturation or until 18 months after the start of the study, in which metabolic expenditure will be assessed in all 3 cases: passive external overheating, thermal plate overheating and convective air blanket overheating.

6.2.4. Sample size

Using the GRANMO sample matingc, Version 7.12 was calculated for the difference of media coupled in energy expenditure at rest of the combination of passive and active external (in two methods, by thermal plate and convective air blanket) versus passive external heating.

Accepting an alpha risk of 0.05 and a beta risk of 0.2 in a bilateral contrast, 34 subjects are required to detect a difference equal to or greater than 0.15 units. A standard deviation of 0.3 is assumed. A 5% tracking loss rate has been estimated.

The difference expected to be found in the resting metabolic expenditure rate of at least 0.1 times the GMB. The increase in baseline metabolic expenditure of these patients in studies with burned patients was 1.4 times with standard deviation of 0.2 - 0.32 times. The sample will be adjusted to the standard deviation values presented in the pilot sample.

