6.4.3 Pilot test

A pilot test will be carried out with at least 2 patients to check the proper collection of variables and debugging of errors in the collection methods and the adequacy of the heating application times and inclusion of the variables.

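### Section 6.2.4 sizes the study for a difference of 0.15 but expects at least 0.1 × GMB; on the likeliest reading of the inputs, power for 0.1 is about 45% at the assumed SD

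*Combined protocol and SAP*

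**What the plan says.** All the inputs are in section 6.2.4 of the combined protocol and SAP.

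- **Comparison.** The sample size "was calculated for the difference of media coupled in energy expenditure at rest", that is, for paired means. Passive plus active heating, by two methods (thermal plate and convective air blanket), is compared with passive heating alone.
- **Calculation.** Alpha is 0.05 two-sided, beta 0.2 and loss 5%. The result is that "34 subjects are required to detect a difference equal to or greater than 0.15 units. A standard deviation of 0.3 is assumed". The unit is not named, and the text does not say whether 0.3 is the SD of within-patient differences or of a single measurement.
- **Expectation.** The following paragraph reads: "The difference expected to be found in the resting metabolic expenditure rate of at least 0.1 times the GMB".
- **Cited variability.** Earlier studies in burned patients are summarised as a 1.4-fold expenditure "with standard deviation of 0.2 - 0.32 times". This describes the expenditure itself, not a change within a patient.
- **Adjustment.** "The sample will be adjusted to the standard deviation values presented in the pilot sample". Section 6.4.3 adds: "A pilot test will be carried out with at least 2 patients".

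Section 6.5 plans to compare means by Student t or Mann-Whitney U. It does not say that the test is paired and does not mention multiplicity.

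**The concern.** The difference that fixes the sample size is half as large again as the smallest difference the plan expects (0.15/0.10 = 1.5). The only power stated is for the larger one. No section says why 0.15 was chosen or what the power is at 0.1.

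If the true effect lies near the expected minimum and the SD is near the assumed 0.3, the study would miss it more often than find it. A reader of 6.2.4 would not know this and could take a null result as evidence against an effect of that size.

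The pilot adjustment does not settle the matter. It changes the SD only and does not say which difference goes with it.

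**Working it through.** **Inputs.** From 6.2.4: two-sided alpha 0.05 (z = 1.960), power 80% (z = 0.842), differences d of 0.15 and 0.10, SD 0.3, cited SD range 0.2 to 0.32, loss 5%. Assumed here: 0.15, 0.10 and the SDs are all in GMB multiples, and 0.3 is the SD of within-patient differences.

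**1. The plan's own figure.** n = [(1.960 + 0.842) × SD/d]².

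- d = 0.15, SD 0.3: (2.802 × 2)² = 31.4, so 32 evaluable; 32/0.95 = 33.7, so 34. This reproduces the plan.
- If 0.3 were the SD per condition with zero correlation, n would be 62.8 before loss. So 34 needs 0.3 as the paired SD or, equivalently, a single-measurement SD with correlation 0.5.

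**2. The other pair of inputs in the same section.**

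- d = 0.10, SD 0.2: the ratio SD/d is again 2, so 31.4, 32 and 34 as before.
- d = 0.10, SD 0.3: (2.802 × 3)² = 70.6, so 71; 71/0.95 = 74.7, so 75 enrolled.

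**3. Power** (paired t test, noncentral t with noncentrality d√n/SD, two-sided 0.05).

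| Difference | SD of differences | 32 evaluable | 34 evaluable |
|---|---|---|---|
| 0.15 | 0.30 | 78% | 81% |
| 0.10 | 0.20 | 78% | 81% |
| 0.10 | 0.25 | 59% | 62% |
| 0.10 | 0.30 | 45% | 47% |
| 0.10 | 0.32 | 40% | 42% |

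With 32 evaluable, power for 0.10 falls below 50% once the SD exceeds about 0.28.

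**4. If 0.3 is a single-measurement SD.** The SD of differences is 0.3 × √[2(1 − ρ)]. The plan gives no correlation ρ, so a range is assumed.

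| ρ (assumed) | SD of differences | Power for 0.10, 32 evaluable |
|---|---|---|
| 0.3 | 0.355 | 34% |
| 0.5 | 0.300 | 45% |
| 0.7 | 0.232 | 65% |
| 0.8 | 0.190 | 82% |

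**5. Two active methods.** If both are compared with passive heating and alpha is split in two (0.025 each, an assumption), power for 0.15 at SD 0.3 with 32 evaluable is about 68% per comparison.

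**6. Pilot adjustment.** The 95% limits for an SD, as multiples of the observed value, are √(df/χ²). With 2 patients (df = 1) they are 0.45 and 32. As an illustration, suppose the adjustment keeps 0.15, may go down, and the pilot SD is 0.2. Then n = (2.802 × 0.2/0.15)² = 13.95, so 14 evaluable, and 14/0.95 gives 15 enrolled. Power for 0.10 at that SD would fall from 78% (32 evaluable) to 41% (14).

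**7. Room to enlarge.** Section 6.2.2 reports "30 patients admitted in 2018 for thermal burns", and section 6.2.3 recruits "until sample saturation or until 18 months after the start of the study". If that rate holds, 30 × 1.5 = 45 admissions before eligibility is applied. That is fewer than the 75 in step 2.

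**The case against.** **The two statements are compatible.** An expected difference of at least 0.1 is a lower bound, and a study may be sized for 0.15 above it. This stands: the text is not a formal contradiction. A reader might infer that the plan claims 80% power for 0.1, or that 34 is wrong. Neither follows. The 80% is attached to 0.15, and 34 is correct for it.

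**The 45% depends on unstated inputs.** This also stands. The unit is undefined, the type of SD is undefined, and the figure moves from 34% to 82% with the assumed correlation. At the cited SD of 0.2, 34 patients do nearly cover 0.1. But 0.2 is the favourable end of the range, and 0.3 is the value the plan assumes.

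**The wording is rough.** The sentence on 0.1 has no main verb, and a link between the two figures may have been lost in translation. That is a reason to ask the sponsor which inputs were meant, not to assume an answer.

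**The pilot scenario is hypothetical.** A reader might infer that the pilot will cut enrolment to 15. The plan does not say that N may fall, or that 0.15 is used. The case shows only what the open wording allows.

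**Misreading a null result depends on reporting.** Partly right: section 6.5 mentions 95% confidence intervals. With 32 patients and SD 0.3 the half-width is 2.04 × 0.3/√32 = 0.108, so an interval centred on zero would still just include 0.1. Reported intervals would help, but 6.2.4 should not leave the reader to work this out.

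**Even 34 may be hard to reach.** It is 34/45, or 76%, of the projected admissions, before the severity and ventilation criteria. That is a fair caution, and a further reason not to ask for more patients.

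**Conclusion.** The point holds as an unreconciled pair of target differences that should be fixed in the text. The stated 80% power belongs to 0.15. For the plan's own minimum expected difference of 0.1, power at the assumed SD is about 45% with 32 evaluable patients (47% with 34), and between 78% and 40% over the cited SD range.

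This rests on two assumptions: that the units are GMB multiples, and that 0.3 is the SD of within-patient differences. The second is supported because it reproduces 34; the first is plausible because the cited SDs are given as multiples. Neither is stated, so confidence is medium.

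The documents also do not show which pair was intended. The pairs 0.15 with SD 0.3 and 0.1 with SD 0.2 give the same 34.

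**What to change.** Keep 34, and make these changes.

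1. **Sponsor confirmation.** State the units of 0.15 and 0.3, whether 0.3 is the SD of within-patient differences, and which pair was intended: 0.15 with SD 0.3, or 0.1 with SD 0.2. If 0.3 is a single-measurement SD, state the assumed correlation.
2. **Section 6.2.4, one target.** For example, if the first pair is confirmed: *34 patients (32 evaluable) give about 80% power for a difference of 0.15 × GMB at an SD of within-patient differences of 0.3, for each active-versus-passive comparison, paired test, two-sided 0.05, without multiplicity adjustment.* If alpha is to be split in two, give about 68% instead.
3. **Section 6.2.4, sensitivity.** Report power for 0.1 × GMB over SD 0.2 to 0.32 (78% to 40% with 32 evaluable).
4. **Pilot adjustment.** State that it uses the SD of within-patient differences and the same target difference, and does not lower N below 34.
5. **Section 6.5.** For the within-patient comparison, name the paired t test or the Wilcoxon signed-rank test, to match the paired calculation.

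The cost is protocol wording and one confirmation, with no patients beyond those planned. The downsides are a less favourable stated power and no cut in N after the pilot. If 0.1 is confirmed as the target, an upward adjustment to a pilot SD of 0.3 would call for 75, against about 45 projected admissions; the sponsor should weigh that before choosing the pair.

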6.2.5. Inclusion criteria

- Patients over the age of 18.
- Patients with thermal burns.
- Patient with high burn criteria according to ABA:
 - o 2nd grade burn
 - Patient 18 59 years: SCQ > 20 %
 - Patient > 60 years or pathology: SCQ > 10 %
 - o 3rd degree burn
 - SCQ > 10 %
- Patients in mechanical ventilation.

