6.2.6 Exclusion criteria

- Sepsis criteria according to ABA.
- Application of debridenenzymatic (data in the next 24 hours).
- 6 hours after surgery.
- After 2 hours after healing the burns

Patients in hemorrhagic shock.

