6.4. Instruments collecting information

Climate comfort measurement

Testo® 435 multifunction air conditioning meter, which performs the necessary measurements to adjust the ventilation and air conditioning systems⁷⁵. The different pluggable sensors and probes will provide the variables to study::

- Thermal speed probe: air speed and volumetric flow rate.
- IAQ (Indoor Air Quality) probe to evaluate air quality measures CO2, ambient temperature, ambient humidity and absolute pressure.
- Balloon probe to measure thermal radiation
- Temperature probe to measure ambient temperature, indoor temperature and surface temperature. Both with measurement accuracy +/- 0.1 oC
- Location of measures
 - At patient bed level:
 - 4 measurement points and extrapolate the results assuming radiant symmetry conditions, would allow to extrapolate results to the entire object area: patient's head and trunk and staff positions at the patient's head and trunk height
 - 2 radiant plate positions: the nearest (50 cm) and 1 meter, distance when the worker's position is simulated in the patient's environment.
 - At the worker's level: 2 positions, at the bedside and on the patient's trunk 50 cm from the center of the bed.
 - Media of the convective air blanket in the functions of 380 and 43oC, calculating temperature, humidity and speed..

Calculation of metabolic expenditure by Indirect Calorimetry and Temperature:

- o Carescape R860® of Datex Ohmeda CE certified with the GE Healthcare Adult D-Lite+ Spirometry Kit with CE 0537 certification. GE CARESCAPE™, is a fan that has an integrated module that can measure the energy expenditure of patients through indirect calorimetry⁷⁶.
- Central temperature:
 - Vesical probe with 16fr MDCON SV temperature sensor registered in Philips Monitor®
 IntelliVue MP5.
- Body temperature:

0

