6.4.2 Data collection

For the analysis of thermal comfort, the suppliedam biennage temperatureshall be analysed in the values: minimum of 25oC, 28oC, 31oC as shown in Table 6... The ambient temperature of 33oC is obvious, as it is considered that in combination with the elements of active external overheating average conditions of 33oC are reached. The graphical representation of the

Table 6: Scenario of combination analysis of heating methods

	Ambient temperature		
Registration No.	25oC	28oC	31oC
Thermal plate at 50 cm	1	3	5
Thermal plate at 100 cm	2	4	6
Convective air blanket 38oC			
Convective air blanket 43oC			

measures shall be carried out as represented in *Annexess IV* and *V*.

The convective air blanket, by the heating mechanism, an analysis will be carried out, studying the theoretical effect combined with the ambient temperature.

Sociodemographic and nutritional data of the patient will be collected after acceptance and signature of the informed consent that will be collected in the first days after the patient's entry into the burn unit. Variables will be collected during the night shift (22:00 to 8:00) because there are no scheduled tasks of cures, diagnostic tests or surgical intervention that may alter both the care activity in the unit and the alteration of variables to be collected. Data will be collected for 6 hours from the intervention: evolution of body and central temperature and metabolic expenditure calculated in 24 hours. From the third day after the burn, the 3 heating methods will be applied to study, on three consecutive nights

Study Protocol, Statistical Analysis Plan (SAP), Informed Consent Form (ICF). Version 1.0

Night 1: Ambient temperature 32oC

Night 2: Ambient temperature and combination with thermal plate

Night 3: Ambient temperature and combination with thermal blanket.

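### One unsourced 5% loss figure covers two contrasts with unequal exposure to loss, and section 6.5 has no analysis for patients who miss a night

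*Combined protocol and SAP*

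**What the plan says.** Section 6.2.4 sizes the study for a paired difference in resting energy expenditure, active plus passive heating against passive heating. "Accepting an alpha risk of 0.05 and a beta risk of 0.2 in a bilateral contrast", it concludes that "34 subjects are required to detect a difference equal to or greater than 0.15 units". It adds "A standard deviation of 0.3 is assumed" and "A 5% tracking loss rate has been estimated". No source is given for the loss rate. The pilot is to update the standard deviation, and nothing is said about updating the loss rate.

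Section 6.2.3 has energy expenditure assessed under all three conditions. Section 6.4.2 states that "the 3 heating methods will be applied to study, on three consecutive nights", from the third day after the burn: ambient temperature on Night 1, plate added on Night 2, blanket added on Night 3. No other order is described.

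Section 6.2.5 lists "Patients in mechanical ventilation" as an inclusion criterion. Section 6.4 describes the ventilator as having an "integrated module that can measure the energy expenditure of patients through indirect calorimetry", and no other calorimeter is named. Section 6.2.6 lists "Sepsis criteria according to ABA" and haemorrhagic shock as exclusions, without saying whether they are checked again each night.

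Section 6.5 compares means by Student t or Mann-Whitney U, depending on the distribution. It does not say whether the t test is paired, and it has no rule for a missing night.

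**The concern.** Calorimetry depends on the patient remaining on the ventilator, so extubation or death ends measurement. Because the order never changes, such losses accumulate on the blanket contrast: it is exposed to two between-night intervals, the plate contrast to one. A single loss figure cannot describe both.

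The analysis section makes this matter more. The sample size assumes paired data, but Mann-Whitney U is a two-sample test. Applied to Night 3 against Night 1, it compares everyone measured at the start with those who remain. If leaving is related to a patient's general metabolic level, part of the difference is a change in who is measured. A paired test avoids that but drops any patient who lacks one of the two nights. At stake are the precision of the blanket result and, under the unpaired reading, its validity.

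**Working it through.** **Inputs.** From 6.2.4: two-sided alpha 0.05, power 0.80, difference 0.15, SD 0.3 (taken as the SD of the paired difference), loss 5%, N = 34. From 6.4.2: fixed order over three nights, hence two intervals. Losses of 5, 10 and 15% per interval are assumptions, because the documents give no extubation, death or sepsis rate.

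**1. The plan's figure.** n = (1.960 + 0.842)² × 0.3² / 0.15² = 31.4, so 32 pairs. 32 / 0.95 = 33.7, so 34. The stated N reproduces.

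**2. What 5% allows.** If loss is permanent and 5% refers to Night 3, the loss per interval is 1 − 0.95^(1/2) = 2.5%.

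**3. Pairs and power by device.** With loss h per interval, plate pairs = 34(1 − h) and blanket pairs = 34(1 − h)². Power by the plan's normal approximation is Φ(0.15/0.3 × √pairs − 1.960).

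| h | Lost by Night 3 | Plate pairs | Plate power | Blanket pairs | Blanket power |
|---|---|---|---|---|---|
| 5% | 9.8% | 32.3 | 81% | 30.7 | 79% |
| 10% | 19% | 30.6 | 79% | 27.5 | 75% |
| 15% | 28% | 28.9 | 77% | 24.6 | 70% |

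For example, at 10% the blanket has 0.5 × √27.5 − 1.960 = 0.66, and Φ(0.66) = 0.75. A noncentral-t calculation gives lower values (plate 79/76/74%, blanket 76/72/66%). It already gives 78% at the planned 32 pairs, so 2 to 4 points of that gap come from the formula and not from losses.

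**4. Bias if loss tracks level.** This is a simulation with assumed between-patient SD 0.25, SD of differences 0.3 and no true difference between nights. The log-odds of loss in each interval change by 1 per SD of the patient's underlying level.

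| Loss per interval | Unpaired Night 3 − Night 1 (absolute bias in means) | Within-patient Night 3 − Night 1 |
|---|---|---|
| 5% | about 0.02 | about 0 |
| 10% | about 0.04 | about 0 |
| 15% | about 0.06 | about 0 |

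The sign follows who leaves: loss of high-expenditure patients makes Night 3 look lower, and loss of low-expenditure patients makes it look higher. A weaker dependence gives a smaller bias.

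**5. Other mechanisms.** If loss depends on the last observed value, again with slope 1 per SD, analysing only patients with all three nights biases the blanket contrast by about 0.006 to 0.018. A model on all nights brings this to about 0. If loss depends on the unobserved change itself, no model on the recorded nights removes the bias. An upper bound is that the whole top fraction f of risers is lost: 0.3 × φ(z)/(1 − f), where z is the upper-f normal quantile. This gives 0.3 × 0.1755/0.90 = 0.06 at f = 10% and 0.3 × 0.2332/0.85 = 0.08 at f = 15%.

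**The case against.** The strongest reply is that nothing in the documents shows 5% to be wrong. The arithmetic is right, no loss rate for these nights is given, and at 5% per interval the blanket's power falls only to about 79%. The same section also uses 0.15 in the calculation but expects a difference of at least 0.1. With SD 0.3, a difference of 0.1 needs 71 pairs (75 with 5% loss), which moves N far more than the loss rate does. All of this stands, and it limits the point.

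It may also be said that Mann-Whitney U uses every available value and so loses nobody. That is true, but it does not help: using everyone on Night 1 and only the remainder on Night 3 is what produces the bias in step 4.

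A reader might infer several stronger things that the text does not support:

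- **Outcome-dependent loss as fact.** It is plausible that extubation, sepsis and death follow severity, but the documents neither state nor quantify it. In a within-patient contrast, dependence on a stable level alone gives no bias.
- **A complete-triplet analysis.** Section 6.2.3 describes what is measured, not an analysis set, so discarding valid plate pairs is not a stated plan. A patient lost after Night 2 still has a plate value.
- **A requirement to stay free of sepsis on all three nights.** Section 6.2.6 lists timing rules that read as checks at each measurement, but nightly re-application of the sepsis and shock exclusions is not stated.

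**Conclusion.** The point holds as a gap in justification and in analysis, not as an error in the sample size. One unsourced 5% covers two contrasts with unequal exposure to loss, and 6.5 has no method for patients with a missing night. The precision cost is modest: over the assumed 5 to 15% per interval, blanket power is about 79 to 70%, against 81 to 77% for the plate. The larger risk is the unpaired test, with a bias of about 0.02 to 0.06 against the 0.15 target. That figure rests on the assumed loss rates, the two SDs and loss that tracks metabolic level. Whether 5% is too low cannot be judged from these documents.

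**What to change.** **Section 6.5.** For energy expenditure, replace Student t and Mann-Whitney U with one linear mixed model on every recorded night, with method as a fixed effect and patient as a random effect. A patient lost before Night 3 then still contributes the ambient and plate values. Report lost nights by method and reason. Add one sensitivity analysis for loss related to unobserved change, which the mixed model does not remove.

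**Section 6.2.4.** Say that 5% by Night 3 allows about 2.5% per interval. Give expected pairs and power separately for plate and blanket over an assumed range, as in step 3, on the plan's own normal approximation. Do not add patients: 30 thermal-burn admissions in 2018 (6.2.2) over 18 months (6.2.3) suggests about 30 × 1.5 = 45, before the ventilation, burn-size and consent filters, and 34 is already 76% of that.

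**Section 6.2.6.** State whether the exclusions apply at each night or only at entry.

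**Cost.** Wording changes, a log of lost nights, slightly more analysis work, and a slightly less favourable stated power for the blanket.

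### The sample size of 34 rests on an SD of 0.3 that the plan neither labels nor supports as a within-patient SD, and a pilot of as few as two patients cannot reset it

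*Combined protocol and SAP*

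**What the plan says.** Section 6.2.4 says the size "was calculated for the difference of media coupled in energy expenditure at rest", which I read as a difference of paired means. Section 6.2.3 fits that reading, since each patient is assessed under all three heating conditions, and section 6.4.2 places these on three consecutive nights.

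The stated inputs are two-sided alpha 0.05, beta 0.2 and 5% loss, with the result that "34 subjects are required to detect a difference equal to or greater than 0.15 units". On variability the plan says only "A standard deviation of 0.3 is assumed", without stating what this SD measures. A separate paragraph gives the sole evidence: the increase in basal expenditure "in studies with burned patients was 1.4 times with standard deviation of 0.2 - 0.32 times". The same paragraph expects a difference of at least 0.1 times basal expenditure.

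It ends: "The sample will be adjusted to the standard deviation values presented in the pilot sample". Section 6.4.3 sets the pilot size: "A pilot test will be carried out with at least 2 patients". The purpose given there is to check data collection and application times. Neither section says which SD the pilot should supply, or sets a larger minimum pilot or a recalculation rule.

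**The concern.** A paired calculation needs the SD of each patient's difference between two nights. The SD of the level across patients is a different quantity, and the two coincide only when the correlation between nights is 0.5. The plan gives no correlation, repeatability figure or SD of change. A reader cannot tell whether 34 patients give the stated power, much less, or much more.

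The plan's remedy makes this worse. An SD from two patients carries almost no information, yet the text as written lets it replace the planning value. A sample size that happened to be right could be cut or inflated by chance.

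**Working it through.** **Inputs from section 6.2.4:** difference 0.15; SD 0.3; two-sided alpha 0.05; power 0.80; loss 5%; cited level SD 0.2 to 0.32. **From section 6.4.3:** pilot of at least 2. **Assumed:** the within-patient correlation ρ, which the documents do not give and which is shown as a range.

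**1. Reproduce the plan's figure.** With 0.3 as the SD of differences, n = (0.3 × 2.8016 / 0.15)² = 31.4, rounded up to 32; 32 / 0.95 = 33.7, rounded up to 34. This matches. With 0.3 as a per-night SD and ρ = 0, the same formula gives 63 completers and 67 with loss. By the exact paired t, 32 completers give 78% power and 34 completers give 81%.

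**2. Link the two SDs.** SD of differences = level SD × √(2(1 − ρ)). At ρ = 0.5 the multiplier is 1.

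**3. Power for a difference of 0.15 with 32 completers (exact paired t):**

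| Level SD | ρ = 0 | ρ = 0.3 | ρ = 0.5 | ρ = 0.7 | ρ = 0.8 |
|---|---|---|---|---|---|
| 0.20 | 83% | 94%* | 98% | >99% | >99% |
| 0.30 | 49% | 64% | 78% | 94% | 99% |
| 0.32 | 44% | 58% | 73% | 91% | 98% |

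*93.5% before rounding.

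**4. The other difference named.** For 0.1 with an SD of differences of 0.3, 32 completers give about 45% power. No correlation is assumed here.

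**5. Precision of a two-patient pilot.** The 95% CI for an SD on k degrees of freedom is the estimate times √(k / χ²) at the 97.5% and 2.5% points.

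- One paired contrast, k = 2 − 1 = 1: factor 0.45 to 31.9.
- Three nights pooled, k = (2 − 1)(3 − 1) = 2: factor 0.52 to 6.3.

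**6. What the adjustment rule would do.** Suppose the true SD of differences is 0.3, so the right number is 32 completers before loss. The recalculated number is 31.4 × χ²(k)/k.

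- k = 1: median 31.4 × 0.455 = 14.3, rounded up to 15. The chance of at least halving is P(χ² < 0.5) = 52%, and of at least doubling is P(χ² > 2) = 16%.
- k = 2: median 31.4 × 0.693 = 21.8, rounded up to 22. The chance of at least halving is 1 − e^(−0.5) = 39%, and of at least doubling is e^(−2) = 14%.

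**7. A later re-estimate.** Twelve complete patients give 11 degrees of freedom for one contrast and a CI factor of 0.71 to 1.70.

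**The case against.** The strongest reply is that nothing has been miscalculated. The plan names a paired comparison, and 0.3 entered as the SD of differences gives exactly 34. The plan does not say that 0.3 came from the 0.2 to 0.32 range, nor that this range is between patients. What the cited studies reported cannot be checked here. This stands. A reader might infer that the plan put a between-patient SD into a paired formula. The documents make that plausible, because 0.3 lies inside the only range offered, but they do not establish it.

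A reader might also infer that the study is underpowered. That is not supported either. At level SD 0.2, 32 completers keep 83% power even with no correlation, and a marked shortfall needs both an SD near the top of the range and a correlation below about 0.5.

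On the pilot, two is a minimum, its stated purpose is mainly operational, and pooling three nights gives 2 degrees of freedom instead of 1. All of this is fair, but nothing requires more than two patients and the pooled interval is still very wide. The 18-month limit in section 6.2.3, with 30 thermal-burn admissions in 2018 (30 × 1.5 = 45 before eligibility is applied), would cap an upward revision. It would not protect against a chance reduction.

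**Conclusion.** The concern holds in two parts.

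First, the 80% power is unsupported, in an unknown direction. It depends on 0.3 being the SD of within-patient differences, which the plan neither states nor justifies. Across the cited SDs and correlations from 0 to 0.8, power for 0.15 runs from 44% to over 99%. The correlation range is an assumption, as is reading the cited SDs as spreads of the level. This is a gap in justification; 34 is not an arithmetic error.

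Second, and more firmly, the rule to adjust the sample to the pilot SD is unsound when the pilot may be two patients. This does not depend on where 0.3 came from. Even if 0.3 is exactly right, the rule has a median result of about 15 completers (22 with pooling) against 32.

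**What to change.** In section 6.2.4:

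- State that 0.3 is an assumed SD of within-patient differences. State that 34 enrolled (32 completers) give about 80% power (78% by exact paired t) for a difference of 0.15 only if that SD holds.
- Tabulate power over level SDs 0.2 to 0.32 and correlations 0 to 0.8, and give the power for the 0.1 difference (about 45% at SD 0.3).
- Remove the adjustment to the pilot SD, leaving the pilot its operational purpose in section 6.4.3.
- Re-estimate the SD of paired differences once, after about 12 patients have completed all three nights, without using the mean difference. Restate the power from that SD and do not reduce the sample below 34.

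The cost is protocol wording and one variance calculation on data already being collected. The stated power becomes conditional and may look less favourable. The re-estimate is only moderately precise: 0.71 to 1.70 on the SD is about 0.5 to 2.9 on the sample size (0.71² and 1.70²). It should therefore inform the power statement and not drive a cut.
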